## 10 TREATMENTS

The IPs are supplied by Swedish Match.

### 10.1 Identity of test products

The test products that will be used in the study are detailed in [Table 10.1-1](#).

**Table 10.1-1 Identity of IPs**

IP	Nicotine content
ZYN Dry Smooth	6 mg nicotine/pouch
ZYN Dry Cool Mint	6 mg nicotine/pouch
ZYN Dry Citrus	6 mg nicotine/pouch
ZYN Moist Smooth	9 mg nicotine/pouch
ZYN Moist Cool Mint	9 mg nicotine/pouch
ZYN Moist Citrus	9 mg nicotine/pouch

### 10.2 Manufacturing and packaging of the IPs

All IPs are manufactured and packaged by Swedish Match in compliance with the Swedish law on food production. Production sites and batch IDs for the IPs will be documented in the TMF. IPs will be shipped by Swedish Match directly to the research clinic (Department of Cariology, Institute of Odontology, Sahlgrenska Academy, University of Gothenburg, Gothenburg, Sweden).

### 10.3 Conditions for storage

All IPs will be stored at room temperature (20-25 °C) in an access-restricted storage area at the Department of Cariology.

### 10.4 Preparation and accountability

The IPs will be distributed according to the randomization list by the site personnel. The Investigator will maintain a storage and accountability log as well as a distributing log detailing the dates and quantities of study IPs provided to each subject, as well as any IPs returned to the Sponsor at the end of the study. Products deliberately and/or accidentally destroyed by the site or the subject must be accounted for.

### 10.5 Treatment administration

The subjects will exchange their tobacco-based snus with the randomized ZYN product and will be instructed to use the products ad libitum, following their regular pattern of use. The compliance will be checked by asking the subjects. The subjects will electronically register the number of pouches used per day, the time points, and the estimated usage time. There will

be a variation in flavors of the products offered. The pouches will be placed in the upper vestibulum.

#### **10.6 Treatment compliance**

Any unused study product will be collected and kept at site until returned to the Sponsor. The Monitor will perform a final IP accountability reconciliation at the end of the study to verify that all unused IP have been returned to the Sponsor and documented.

## 11 STUDY ASSESSMENTS

The study assessments are described in the sections below and the timing of these assessments are detailed in the schedule of events, Section [8.1 \(Table 8.1-1\)](#).

### 11.1 Recording of data

The PI will provide the Sponsor with all data produced during the study from the scheduled study assessments. The PI ensures the accuracy, completeness, legibility, and timeliness of the data reported to the Sponsor in the eCRF and in all required reports.

The different study assessments will be collected in order:

1. Dental plaque acidogenicity
2. Amount of plaque
3. Pooled dental plaque (cariogenic microorganisms)
4. Collection of saliva
5. Oral mucosa lesions
6. Tooth discoloration
7. Biopsy

The subjects will be scheduled for 4 treatment visits (Visit 2-5), Day -28, Day 0, Day 14, and Day 28. The allowed time deviation for these visits is  $\pm 2$  days. The subjects will collect the morning urine and transfer it to the clinic on Visit 3 and Visit 5. For plaque acidogenicity, assessments will be performed before and after a mouth rinse with 10% sucrose for 1 min and pH will be measured in the plaques at the time points 0, 2, 5, 10, 15, 30, 45, and 60 min. Allowed deviations for these time points are  $\pm 1$  min for the time points 0-15 min and  $\pm 2$  min for the time points 30-60 min.

### 11.2 Demographics and other baseline characteristics

#### 11.2.1 *Informed consent*

Signed informed consent must be obtained before any screening procedures are initiated. The informed consent procedure is further described in Section [14.3](#).

#### 11.2.2 *Demographic information*

The following demographic data will be recorded: gender, age, ethnicity, and race.

#### 11.2.3 *Medical/surgical history*

Medical/surgical history will be obtained by subject interview in order to verify that the eligibility criteria are met.

#### 11.2.4 *History of nicotine use*

The history of nicotine uses in terms of brands, average consumption per day during the last 30 days, and duration of use (years), and history of smoking (cigarettes and e-cigarettes) will be obtained by subject interview.

#### 11.2.5 *Eligibility criteria*

Eligibility criteria should be checked during screening and verified before randomization on Visit 3. The criteria are specified in Sections [9.4](#) and [9.5](#).

#### 11.2.6 *Oral examination*

A brief oral examination will be performed at screening (Visit 1) and include assessments of overall good oral health status, normal stimulated salivary secretion rate (>0.7 mL/min), and at least 24 own teeth remaining. A brief oral examination will also be performed at each treatment visit to ensure overall good oral health status.

#### 11.2.7 *Pregnancy test*

All female subjects of childbearing potential will do a urine pregnancy test at screening (Visit 1) as well as at the discretion of the Investigator during the treatment visits (Visit 2-5).

#### 11.2.8 *Baseline symptoms*

A baseline symptom is defined as an event that occurs between the subject's signing of the ICF until the start of the randomization on the second treatment visit (*i.e.*, an event that occurs when the subjects are using their tobacco-based snus). Such events are not AEs and will be recorded as baseline symptoms in the Medical History Log in the eCRF.

#### 11.2.9 *Prior and concomitant medication*

Prior and concomitant medications taken within 2 weeks prior to screening will be obtained by subject interview for documentation of the subject's status regarding current medications.

Medications will be classified as prior if the stop date was before or on the day of the randomization, prior to start of study product use, and as concomitant if ongoing on the day of the second treatment visit (Visit 3), started or stopped after the assessments on that visit. To distinguish between prior and concomitant medications on the second treatment visit (Visit 3), the start time of any newly introduced medication or the stop time of any previously ongoing medication must be recorded in the eCRF.

Any use of concomitant medication from screening until the last treatment visit (Visit 5) will be documented appropriately in the subject's eCRF. Relevant information (*i.e.*, name of medication, dose, unit, frequency, start and stop dates, reason for use) must be recorded. All changes in medication will be noted in the eCRF.

### 11.3 **Assessment related to the primary endpoint**

#### 11.3.1 *Dental plaque acidogenicity*

An iridium microelectrode will be inserted into the plaque on two buccal surfaces in the upper jaw and two approximal surfaces in the upper and lower jaw. The electrode will be connected to a pH meter (Orion SA720 pH/ISE Meter) to which also a reference electrode will be connected. The reference electrode is placed into a solution of 3 M KCl to which the subject's finger is placed in order to create a salt bridge. After calibration and baseline assessment (0 min), the subjects will rinse their mouth with 10 mL of a 10% sucrose solution for 1 min and pH will then be measured at eight time points up to 60 min (0, 2, 5, 10, 15, 30, 45, and 60 min). In case of lack of microelectrodes, the strip method will be used; a paper indicator strip

will be inserted in the area and kept in place for 10 sec after which the color change will be manually compared with a color scale.

The date and time of collection of each sample and the assessed pH values will be recorded in the eCRF.

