#### 7.1.1 Primary endpoint

The difference between ZYN Dry and ZYN Moist in terms of changes in dental plaque acidogenicity, assessed by measuring pH in plaques, after substitution of tobacco-based snus for 4 weeks.

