## 17.5 Analysis of the primary endpoint

### 17.5.1 *Difference in dental plaque acidogenicity between ZYN Dry and ZYN Moist*

The primary endpoint is the difference between ZYN Dry and ZYN Moist in terms of changes in dental plaque acidogenicity, assessed by measuring pH in plaques, after substitution of tobacco-based snus for 4 weeks. Assessment of dental plaque acidogenicity will be described using AUC6.2 to the observed dental plaque acidogenicity and presented using summary statistics as described in Section [17.1](#).

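### The primary plaque pH may switch from microelectrode to an eye-read colour strip with no one-method-per-subject rule and no method among the listed data items, so a subject's change in AUC6.2 can contain a method difference of unknown size

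*Protocol*

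**What the plan says.** Protocol section 11.3.1 sets the default: "An iridium microelectrode will be inserted into the plaque on two buccal surfaces in the upper jaw", plus two approximal surfaces, with the electrode connected to a pH meter and calibrated first. The same section then gives a fallback: "In case of lack of microelectrodes, the strip method will be used". The strip stays in place for 10 seconds, after which "the color change will be manually compared with a color scale". Supply is the only stated trigger. No condition ties the method to the subject, the visit or the arm, and no agreement or conversion between methods is given.

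On data capture the section says: "The date and time of collection of each sample and the assessed pH values will be recorded in the eCRF". The method used is not in that list.

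The primary endpoint (section 7.1.1) is "The difference between ZYN Dry and ZYN Moist in terms of changes in dental plaque acidogenicity, assessed by measuring pH in plaques", after four weeks of substitution. Section 17.1 defines baseline as the last data before randomization, which is Visit 3. Section 17.5.1 has acidogenicity "described using AUC6.2 to the observed dental plaque acidogenicity" and presents it with summary statistics. Secondary endpoint 1 uses the same measurements (sections 11.4.1 and 17.6.1). Section 9.9 makes the study open-label with no blinding.

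**The concern.** The protocol's own description shows that the two methods are not interchangeable: one is a calibrated meter reading, the other a colour match judged by eye. If a subject has an electrode at Visit 3 and a strip at Visit 5, or the reverse, the change score is the product effect plus the instrument difference, and the two cannot be separated within that subject.

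AUC6.2 makes this worse than a single pH reading would. Any constant offset is accumulated over every minute the curve lies below 6.2, so an offset that looks small in pH units becomes a sizeable area. With about 20 evaluable subjects per arm (section 17.2), a few mixed-method subjects can move an arm mean visibly. If the method is not captured, no later analysis can identify them.

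**Working it through.** **What the protocol supplies.** The pH time points are 0, 2, 5, 10, 15, 30, 45 and 60 min (section 11.1) and the threshold is 6.2 (section 17.5.1). It states no product effect, no SD and no strip-electrode difference, so there is no figure on this point to reproduce. The curves and offsets below are assumptions.

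**Formula.** AUC6.2 = integral over 0 to 60 min of max(6.2 − pH, 0), with linear interpolation.

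**Illustrative curve.** pH 6.9, 5.9, 5.4, 5.3, 5.4, 5.8, 6.1, 6.4. Depth below 6.2: −0.7, 0.3, 0.8, 0.9, 0.8, 0.4, 0.1, −0.2. By segment:

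- 0–2 min: below 6.2 for the last 0.6 min, 0.6 × 0.3 / 2 = 0.09
- 2–5 min: 0.55 × 3 = 1.65
- 5–10 min: 0.85 × 5 = 4.25
- 10–15 min: 0.85 × 5 = 4.25
- 15–30 min: 0.60 × 15 = 9.00
- 30–45 min: 0.25 × 15 = 3.75
- 45–60 min: below 6.2 for the first 5 min, 5 × 0.1 / 2 = 0.25

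Total: 23.24 pH·min.

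**Method offset at one visit only.** Adding a constant strip-minus-electrode offset to all eight points gives:

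| Offset (pH) | Shift in AUC6.2 (pH·min) | Share of 23.24 |
|---|---|---|
| −0.1 | +5.12 | 22% |
| −0.2 | +10.76 | 46% |
| −0.3 | +16.67 | 72% |
| +0.1 | −4.60 | 20% |
| +0.2 | −8.68 | 37% |
| +0.3 | −12.24 | 53% |

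**Dependence on the curve.** Three other assumed curves were used:

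- shallow: 6.9, 6.3, 6.0, 5.9, 6.0, 6.3, 6.6, 6.8; AUC6.2 3.7
- mid: 6.8, 6.0, 5.6, 5.5, 5.6, 6.0, 6.4, 6.7; AUC6.2 14.5
- deep: 6.6, 5.6, 5.2, 5.0, 5.1, 5.5, 5.9, 6.3; AUC6.2 36.7

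An offset of 0.2 pH in either direction shifts these by 3.2–5.6, 6.4–8.0 and 10.3–11.7 pH·min. Rounding the same curves to steps of 0.2, 0.3 or 0.5 pH with no offset moves the AUC by at most about 1.4. On these curves a systematic difference between methods matters much more than a coarse scale.

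**Does holding one method help?** Suppose the true improvement from Visit 3 to Visit 5 is 0.1 pH on the illustrative curve, so the true change is −4.60.

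- Strip at both visits, offset +0.2: −12.24 − (−8.68) = −3.56.
- Strip at both visits, offset −0.2: 5.12 − 10.76 = −5.64.
- Strip at Visit 5 only, offset +0.2: the curve is raised by 0.3, giving −12.24.
- Strip at Visit 5 only, offset −0.2: the curve is lowered by 0.1, giving +5.12, the wrong sign.

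One method at both visits removes most of the error. Cancellation is incomplete because the area is cut off at 6.2.

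**Arm level.**

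- Within an arm, distortion of mean change = share switched at one visit × shift. For example, 25% switched at Visit 5 with offset −0.2 gives 0.25 × 10.76 = 2.69 pH·min.
- Between arms, bias = difference between arms in share switched × shift. A shift of 1 SD in 25% of one arm only gives 0.25 SD.
- With 25% switched in both arms, the mean bias is zero and the SD rises by a factor √(1 + 0.25 × 0.75 × 1²) = 1.09.

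**The case against.** The strongest reply is that this is a contingency clause that may never be used, in a study with randomized arms and a descriptive analysis. A shortage of electrodes is a supply event with no stated link to arm, so switching should fall on both arms alike and cost precision, not validity. The protocol defers technical detail to a separate SAP, and section 17.5.1 does not say how electrode and strip values would be combined. The eCRF itself is not shown either, so a method field may exist. At Visit 3 the pH measurement precedes randomization, so arm cannot influence a baseline strip reading.

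Most of this stands, and it limits the point. The arm comparison is little exposed to bias unless switching differs by arm, and unblinded reading is an issue only at Visits 4 and 5. It does not remove the point. Which instrument is used at a visit is a measurement rule belonging to section 11.3.1. A SAP can handle mixed-method data only if the method was recorded, and the protocol's list of recorded items omits it.

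A reader might infer that the method difference would exceed the product effect. The documents do not support that: neither quantity is stated, and section 17.2 says data on the two product types are lacking. A reader might also infer that shortages would fall mainly on follow-up visits. Nothing indicates this. If entry is staggered over the planned study period, one subject's Visit 5 can coincide with another's Visit 3.

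**Conclusion.** The point holds in limited form. As written, section 11.3.1 lets a subject's primary change score mix two measurement methods. It neither prevents this nor lists the information needed to detect it. The resulting error is of unknown size. Under assumed offsets of 0.1 to 0.3 pH and one illustrative curve it is about 5 to 17 pH·min against a base of 23; other assumed curves give different absolute shifts and different shares.

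The consequences, in order of certainty:

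- added noise in the between-arm comparison whenever subjects switch;
- distorted within-arm change if switches are concentrated at one visit;
- bias between arms only if switching differs by arm;
- room for observer influence in strip readings after randomization.

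How often the fallback would be used is not known. This is a worthwhile, inexpensive improvement to the primary measurement, not evidence that the comparison is invalid.

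**What to change.** Amend section 11.3.1 so that each subject is measured with the same method at all pH visits (Visits 2 to 5), and at minimum at Visits 3 and 5. To make this workable, reserve electrodes for subjects who started on them, and where electrodes are lacking rebook within the existing ±2 day window (section 11.1) if possible.

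Add the method, electrode or strip, to the items recorded in the eCRF for every measurement.

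In section 17.5.1, keep all randomized subjects in the primary summary, in line with the full analysis set in section 17.3.1. Add a sensitivity summary of the change without subjects whose Visit 3 and Visit 5 methods differ, and do the same for secondary endpoint 1. A method covariate is not proposed, because section 17.5.1 plans summary statistics and has no model for it to enter. Dropping mixed-method subjects from the primary summary is not proposed either, because it would remove randomized subjects.

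Cost: a sentence or two of protocol text, one eCRF field, electrode stock planning and one extra summary. An occasional visit would be rebooked, and the subject would then have to repeat or extend the pre-visit cleaning abstention in section 9.6.1. Rebooking within ±2 days will not outlast a long shortage, so some mixed-method subjects may remain; the recorded method and the sensitivity summary are there for them.

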## 11.4 Assessments related to secondary endpoints

### 11.4.1 *Dental plaque acidogenicity*

The difference in dental plaque acidogenicity, assessed by measuring pH in plaques, following tobacco-based snus substitution with either ZYN Dry or ZYN Moist for 4 weeks will be assessed as described above for the primary endpoint.

### 11.4.2 *Cariogenic microorganisms in dental plaque*

Pooled plaque samples will be collected with a sterile toothpick (19) from the buccal areas of respective quadrants. The samples, handled within 1 h after collection, will be dispersed on a Whirlimixer, diluted in potassium phosphate buffer, and plated in duplicate on different agar plates for analyses of the number of microorganisms related to caries and periodontal diseases. MSB agar will be used for mutans streptococci, MS agar for total streptococci, Rogosa SL agar for lactobacilli, and blood agar for total viable count. After incubation, the number of colony-forming units (CFU) on the agar plates will be counted. For analyses of a broader range of cariogenic microorganisms, gene expression levels will be assessed by quantitative PCR.

The date and time of collection of each sample and the assessed CFUs will be recorded in the eCRF.

### 11.4.3 *Amount of plaque*

The amount of plaque will be measured on all surfaces of the Ramfjord teeth (16, 21, 24, 36, 41, and 46) according to Ramfjord (20). For each tooth, six sites (mesio-buccal, buccal, disto-buccal, disto-lingual, lingual, and mesio-lingual) will be scored from 0-3 according to Silness and Løe (21).

The date and time of collection of each sample and the assessed scores will be recorded in the eCRF.

#### 11.4.5 *Tooth discoloration*

Grading of tooth discoloration of the maxillary and mandibular anterior teeth will be performed on Day -28, Day 0, and Day 28. On Day 0, it will be performed before and after cleaning of the teeth with rotating rubber cup and polishing paste. Grading of discoloration will be assessed by colorimetry using a colorimeter (Minolta Chroma Meter CR-321). Visual shade evaluation will also be performed using a shade guide (VITA Zahnfabrik, Bad Sackingen, Germany).

The date and time of collection of each sample, assessed values by colorimetry and results from shade evaluation will be recorded in the eCRF.

### 11.5 Assessments related to exploratory endpoints

#### 11.5.1 *Biomarkers of exposure in saliva and urine*

BoE (e.g., nicotine, cotinine, and tobacco-specific nitrosamines) will be assessed in saliva and urine. Saliva (spit) will be collected at Visit 2-5. The subjects will collect the morning urine and transfer it to the clinic on Visit 3 and Visit 5. Saliva and urine will be stored at -20°C until analysis.

### 11.6 Adverse events

The PI is responsible for ensuring that all medical staff involved in the study are familiar with the content of this section.

#### 11.6.1 *Definition of adverse event*

An adverse event (also known as adverse experience), abbreviated AE, is defined as any untoward medical occurrence in a subject administered a medicinal product (in this case an IP) and which does not necessarily have a causal relationship with this treatment. An AE can therefore be any unfavorable and unintended sign, symptom, or disease temporally associated with the use of a medicinal product, whether or not considered related to the IP.

#### 11.6.2 *Definition of serious adverse event*

An SAE is any AE which:

- results in death,
- is life-threatening (this refers to a reaction in which the subject was at risk of death at the time of the reaction, it does not refer to a reaction that hypothetically might had led to death if the reaction was more severe),
- requires in-patient hospitalization or prolongation of existing hospitalization,
- results in persistent or significant disability/incapacity,
- is a congenital anomaly/birth defect,
- is an important medical event (IME) (this refers to a reaction that may not be immediately life-threatening or result in death or hospitalization but may jeopardize the subject or may require intervention to prevent any of the other

outcomes defined above).

Examples of IMEs are intensive treatment in an emergency room for allergic bronchospasm or blood dyscrasias, convulsions that do not result in hospitalization, development of drug dependency, and drug abuse.

Planned hospitalizations or surgical interventions for a condition that existed before the subject signed the ICF and that did not change in intensity are not SAEs.

If there is any doubt as to whether an AE meets the definition of an SAE, a conservative viewpoint must be taken, and the AE must be reported as an SAE.

### 11.6.3 *Time period and frequency for collecting adverse events*

All AEs (including SAEs) will be collected by subject interview from the start of substitution of the subject's traditional tobacco-based snus with either ZYN Dry or ZYN Moist on Visit 3 (Day 0) until the last treatment visit (Visit 5, Day 28).

Any AE with start date on the day of the substitution of tobacco-based snus with ZYN must be recorded with start time.

At Visit 5, information on new AEs or SAEs, if any, and stop dates for ongoing events must be recorded as applicable.

Investigators are not obligated to actively seek AEs or SAEs after the conclusion of the study participation. However, if the Investigator learns of any SAE, including a death, at any time after a participant has been discharged from the study, and he/she considers the event to be reasonably related to the study intervention or study participation, the Investigator must promptly notify the Sponsor.

### 11.6.4 *Assessment of intensity*

The grading of the intensity of AEs will follow the Common Terminology Criteria for Adverse Events (CTCAE) v5.0 (23). Grade refers to the severity of the AE. The CTCAE displays Grades 1 through 5 with unique clinical descriptions of severity for each AE based on this general guideline.

The Investigator must assess the intensity of an AE using the definitions in [Table 11.6-1](#), and record it on the AE log in the eCRF.

**Table 11.6-1 Grading of adverse event intensity**

Grade	Definition
Grade 1	Mild; asymptomatic or mild symptoms; clinical or diagnostic observations only; intervention not indicated.
Grade 2	Moderate; minimal, local, or non-invasive intervention indicated; limiting age-appropriate instrumental activities of daily living (ADL)  .
Grade 3	Severe or medically significant but not immediately life-threatening; hospitalization or prolongation of hospitalization indicated; disabling; limiting self-care ADL  .
Grade 4	Life-threatening consequences: urgent intervention indicated.
Grade 5	Death related to AE.

 Instrumental ADL refers to preparing meals, shopping for groceries or clothes, using the telephone, managing money, et c.

 Self-care ADL refers to bathing, dressing, and undressing, feeding self, using the toilet, taking medications, and not being bedridden.

